3.8.2.1.2. Sensitivity Analysis

To assess the robustness of the primary analysis, the following sensitivity analyses will be performed:

- To assess the potential impact of missing data due to missing not at random (MNAR), the delta-adjusted Pattern Mixture Model ([Ratitch et al, 2013](#)) will be conducted to assess the impact of missing data. It incorporates the clinical assumption that OLZ subjects who discontinue at a given time point would have, on average, their unobserved weight gain decreased by some amount δ compared with the observed weight gain of subjects on the OLZ arm who continue to the next time point. Subjects who discontinue from the ALKS 3831 arm would have the same weight gain trajectory as the ALKS 3831 subjects who stay on the study. A sequential regression-based MI procedure will be used to incorporate the assumption and to allow uncertainty in the imputations to be reflected appropriately in the analysis. The imputation model will include the measurement at the current time point as the response variable, and the measurements at the previous time points, the baseline, race (Black or African American, Non-Black or African American), and age (<30, ≥ 30 years) as covariates. Five hundred imputations will be carried out. For each of the 500 imputed data sets, the same ANCOVA model as in the primary analysis will be fitted to the percent change from baseline at Week 24 to obtain the treatment effect estimate and standard error. Rubin's rule will be used to combine the treatment effect estimates and standard errors across imputations. The shift parameters will account for 10%, 20%, 30%, 40%, 50%, and up to 100% of the observed treatment difference between OLZ and ALKS 3831 from the primary analysis of the percent change from baseline in body weight at Week 24 in FAS population.
- To further assess the potential impact of missing data due to missing not at random (MNAR), the primary analysis will be repeated including both on-treatment and off-treatment weight assessments after premature discontinuation of study drug.
- The ANCOVA and MI approach may adjust for additional covariates and/or factors, including but not limited to study region or study sites.
- Average treatment difference across visits through Week 24 between ALKS 3831 and OLZ will be analyzed using mixed model with repeated measurements (MMRM) model. The MMRM model will include treatment, visit, treatment-by-visit interaction term, race (Black or African American, Non-Black or African American) and age (<30, ≥ 30 years) as categorical fixed effects; baseline weight will be included as a covariate. An unstructured covariance structure will be applied. The Kenward-Roger approximation ([Kenward and Roger 1997](#)) will be used to adjust the denominator degree of freedom. The analysis will be performed on all observed post-randomization on-treatment weight measurements without imputation of missing data.

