1.2 Summary of the Study Design

This is a Phase 3, multicenter, randomized, double-blind, study in adults with schizophrenia.

Subjects will be screened at Visit 1, up to 30 days prior to randomization. At Visit 2, eligible subjects will be randomized 1:1 to ALKS 3831 (olanzapine/10 mg samidorphan) or olanzapine treatment groups and receive study drug for up to 24 weeks. Subjects are not excluded from the study if they are taking other antipsychotic medication. However, they must be tapered off this medication and switched onto ALKS 3831 or olanzapine by the end of Week 2, Visit 4. This is an outpatient study in which subjects will visit the study site weekly for the first 6 weeks, then biweekly for the remaining 18 weeks. Study drug will be provided as coated bilayer tablets dispensed to the subjects in blister packs at each visit to be taken at home, one tablet by mouth each day, preferably at bedtime. For the first week, subjects will receive 10 mg olanzapine per dose: either ALKS 3831 10/10 (10 mg olanzapine/10 mg samidorphan) or OLZ 10 (10 mg olanzapine), according to treatment assignment. At the end of Week 1, the dose will escalate to 20 mg: ALKS 3831 20/10 [20 mg olanzapine/10 mg samidorphan] or OLZ 20). Following this increase, the dose may be decreased back to 10 mg at the end of Week 2, 3, or 4 according to investigator discretion. No further dose adjustments will be allowed beyond Week 4 and the dose will remain fixed for the remaining 20 weeks of the study. Body weight and metabolic parameters (including fasting triglycerides, cholesterol, and glucose) will be measured throughout the 24-week treatment period. Psychiatric symptoms will also be evaluated using Positive and Negative Syndrome Scale (PANSS) and Clinical Global Impression (CGI). A schematic summarizing study design is presented below.

Figure 1: ALK3831-A303 Study Design Schematic

Subjects completing this study will be eligible to enroll in a long-term safety study (ALK3831-A304). Subjects not continuing in the long-term safety study or subjects prematurely discontinuing from the study will enter the 4-week safety follow-up period.

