2. SAMPLE SIZE CONSIDERATION

The initial target sample size is 200 randomized subjects per treatment group (400 in total). This sample size will provide at least 90% power to detect a significant difference in mean percent change in body weight at Week 24 of 4% or more (3.0% on ALKS 3831 versus 7% on olanzapine group with standard deviation of 9%) and a 13% difference in proportion of subjects with $\geq 10\%$ weight gain at Week 24 (14% on ALKS 3831 versus 27% on olanzapine group).

An unblinded interim analysis is planned to be conducted to determine if the final sample size will be increased to 540 (270 subjects per treatment group), details in [ALK3831-A303 Interim Analysis Plan](#).

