3.8. Efficacy Analyses

3.8.1. General Considerations

All statistical tests will be 2-sided hypothesis tests performed at the 5% significance level. All confidence intervals will be 2-sided 95% confidence intervals.

Baseline for the primary efficacy analysis is defined as the last non-missing observation on or before the first dose of study drug in the double-blind treatment period.

Only the on-treatment weight assessments will be included in the analyses, unless specified otherwise.

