3.8.2. Primary Efficacy Endpoints

The primary efficacy endpoints are

- percent change from baseline in body weight at Week 24 in FAS population
- proportion of subjects with $\geq 10\%$ weight gain at Week 24 in FAS population

3.8.2.1. Primary Efficacy Endpoint: Percent Change from Baseline in Body Weight at Week 24 in the FAS population

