3.8.2.2.2. Sensitivity analysis

To assess the robustness of the primary analysis of the primary endpoint, the following sensitivity analyses will be performed:

- To assess the potential impact of missing data due to missing not at random (MNAR), the delta-adjusted Pattern Mixture Model in [Section 3.8.2.1.2](#) will be conducted to assess the impact of missing data. Proportion of subjects with $\geq 10\%$ Weight Gain at Week 24 will be derived based on the same complete datasets obtained from the multiple imputation procedure in [Section 3.8.2.1.2](#). The logistic regression model as in the primary analysis will be fitted to obtain the treatment effect estimate and standard error. Rubin's rule will be used to combine the treatment effect estimates and standard errors across imputations.
- To further assess the potential impact of missing data due to missing not at random (MNAR), the approach described in [Section 3.8.2.2.1](#) will be repeated including both on-treatment and off-treatment weight assessments after premature discontinuation of study drug.
- The logistic regression model may also adjust for additional covariates and/or factors, including but not limited to, study region or study sites.
- Average treatment difference across visits through Week 24 between ALKS 3831 and OLZ will be analyzed.

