3.8.3. Key Secondary Endpoint

The key secondary endpoint is the proportion of subjects with $\geq 7\%$ weight gain at Week 24. The primary analysis will be carried out using a logistic regression model based on MI without CHW adjustment as described in [Section 3.8.2.2.1](#). The sensitivity analysis will be the same as [Section 3.8.2.2.2](#).

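### The MMRM listed as a robustness check of the Week 24 percent-change co-primary targets an average over visits, not the Week 24 difference; the binary endpoints repeat this target with no model named

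*SAP*

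**What the plan says.** SAP 3.8.2 defines the first co-primary as "percent change from baseline in body weight at Week 24 in FAS population"; the second, the proportion with ≥10% gain, is also at Week 24. SAP 3.8.2.1.2 opens with "To assess the robustness of the primary analysis, the following sensitivity analyses will be performed". Its last item reads: "Average treatment difference across visits through Week 24 between ALKS 3831 and OLZ will be analyzed using mixed model with repeated measurements". The model has treatment, visit and treatment-by-visit terms and an unstructured covariance. It uses every observed on-treatment weight after randomization, with no imputation. The item does not state which visits enter the average, how they are weighted, or whether the response is percent change or weight.

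For ≥10% gain, SAP 3.8.2.2.2 says only: "Average treatment difference across visits through Week 24 between ALKS 3831 and OLZ will be analyzed". No model is named. A generalized linear mixed model appears in the SAP abbreviation list, but no analysis section uses it. For ≥7% gain, SAP 3.8.3 adds: "The sensitivity analysis will be the same as" section 3.8.2.2.2.

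**The concern.** A sensitivity analysis of a Week 24 result should estimate the Week 24 effect under a changed method or assumption. An average over visits estimates something else. If it comes out smaller than the primary estimate, that could be taken for a lack of robustness when it only reflects earlier time points. If it is significant, it could be taken as confirmation although other visits may drive it.

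For percent change, this is the only planned model-based check that does not use multiple imputation. It is the natural place to see whether the Week 24 estimate depends on the imputation procedure. The treatment-by-visit term makes the Week 24 contrast available from the same fit, but the SAP does not request it. By-visit absolute weight change (SAP 3.8.6) is analyzed by ANCOVA with multiple imputation, so it does not fill the gap.

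**Working it through.** **Inputs.**
- Test level, SAP 3.8.1: "All statistical tests will be 2-sided hypothesis tests performed at the 5% significance level".
- Allocation, SAP 1.2: "eligible subjects will be randomized 1:1 to ALKS 3831" or olanzapine.
- Size, SAP 2: "The initial target sample size is 200 randomized subjects per treatment group (400 in total").
- Week 24 assumptions, SAP 2: mean gain 3% vs 7% (difference 4 points), SD 9; ≥10% gain in 14% vs 27%; stated power at least 90%.
- On-treatment post-baseline weight visits, protocol Table 3: Weeks 1, 2, 4, 6, 8, 12, 16, 20 and 24.
- Not in the documents: the time course of the difference, the between-visit covariance and the visit weights. These are assumed below.

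**The plan's own figures.**
- Means: SE = 9 × √(2/200) = 0.90; 4/0.90 − 1.96 = 2.48; power 99.4%.
- Proportions, pooled: null SE = √(0.205 × 0.795 × 2/200) = 0.0404; alternative SE = √((0.14 × 0.86 + 0.27 × 0.73)/200) = 0.0398; (0.13 − 1.96 × 0.0404)/0.0398 = 1.28; power 89.9%. The unpooled version gives 90.4%.

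The stated power reproduces, and both figures refer to Week 24.

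**What the average targets.** Fix the Week 24 difference at 4 points and let f(t) be the fraction of it reached by week t, with f(24) = 1. With equal weights, the average is 4 × (1/9) × Σ f(t) over the nine visits. The visit weeks sum to 93, so the mean visit is Week 10.3; five of the nine visits fall by Week 8.

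Worked case, linear growth, f(t) = t/24: 4 × 10.33/24 = 1.72.

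For the plateau cases, f(t) = (1 − e^(−t/τ))/(1 − e^(−24/τ)).

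| Assumed course of the difference | Average (points) | Share of Week 24 value |
|---|---|---|
| Linear | 1.72 | 43% |
| Square root of time | 2.41 | 60% |
| Plateau, τ = 8 weeks | 2.53 | 63% |
| Plateau, τ = 4 weeks | 3.03 | 76% |
| Plateau, τ = 2 weeks | 3.48 | 87% |
| Constant from Week 1 | 4.00 | 100% |
| Peak of 1.5 times the Week 24 value at Week 6, then decline | 4.16 | 104% |

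The weights matter too. Weighting by elapsed time (trapezoidal rule, starting from zero at Week 0) moves the linear case from 1.72 to 2.00.

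**What significance of the average would show.** Take the linear case, 1.72 points with 200 per arm.
- Variance growing in proportion to time: SD of the average 4.5, SE 0.45, power 97%.
- Constant SD 9 with correlation 0.8: SD of the average 9 × √(0.8 + 0.2/9) = 8.16, SE 0.816, power 56%.

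The chance of a significant average therefore depends heavily on an unstated covariance. A smaller average need not be a weaker test, and neither outcome says whether the Week 24 difference holds.

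**The case against.** The strongest reply is that little depends on this item. SAP 3.8.4 rests success only on the primary analyses with the CHW adjustment, so the MMRM cannot change the trial's conclusion. The wording openly calls the quantity an average. The other sensitivity analyses in SAP 3.8.2.1.2 (delta-adjusted pattern mixture, inclusion of off-treatment weights, extra covariates) keep the Week 24 endpoint and deal with the main threat, missing data. SAP 3.8.2.1.1 also gives observed-data descriptive statistics at each visit. Finally, a Week 24 MMRM contrast on on-treatment data assumes missing at random, as the primary imputation does, so it would add only a limited check. All of this stands, and it keeps the severity low. It does not remove the mismatch between the stated purpose and the stated target.

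A reader might go further and infer that the average must be smaller than the Week 24 effect. The documents do not support that. It requires a difference that grows over time. Growth is plausible: protocol 5.3 reports 29% less gain at 3 weeks and 37% at 12 weeks, and the planning values imply (7 − 3)/7 = 57% at Week 24. But these figures come from different populations and do not form a time course, and SAP 3.8.2.1.3 treats the timing of weight stabilization as an open question. The 10 mg starting dose in Week 1 and the cross-taper to Week 2 apply to both arms and do not show bias in the contrast.

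A reader might also put a size on the dilution for ≥10% gain with a normal model. Means of 7% and 3% with SD 9 imply about 37% vs 22% above the threshold at Week 24, not the planned 27% vs 14%, so no binary figure is relied on here.

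**Conclusion.** The point holds as a mismatch of target, and it is minor. The MMRM in SAP 3.8.2.1.2 is presented as a check on a Week 24 result but is specified to report an average over visits. That reported result does not directly check the Week 24 estimate. How far the two differ depends on an assumed time course and on equal weighting: from less than half the Week 24 value under linear growth to no difference if the effect is constant from Week 1. The average is smaller only if the difference grows over time.

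For the ≥10% and ≥7% endpoints the same target is stated with no model, so the method is unspecified as well. It would go beyond the text to say that a repeated-measures binary analysis is planned. It would also be too strong to say that robustness at Week 24 goes untested: the limit applies to the averaged contrast, not to the fitted model, which can give a Week 24 contrast, nor to the rest of the sensitivity program.

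**What to change.** - **SAP 3.8.2.1.2:** state that the response is percent change from baseline, and make the sensitivity estimate the Week 24 treatment contrast (LS mean difference with 95% CI) from the same MMRM.
- **SAP 3.8.2.2.2, and so 3.8.3:** name the repeated-measures model for the binary endpoint and use its Week 24 contrast.
- **Both:** keep the average over visits as a supplementary result, with the visits and weights stated.
- **Interpretation:** say that the Week 24 MMRM contrast still assumes missing at random. It checks dependence on the imputation method; departures from that assumption remain the task of the delta-adjusted analysis.

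The cost is a few lines of SAP text, one contrast statement per model and the programming of the binary model once it is named. No new data are needed, and the primary test and sample size do not change.

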3.8.2.1.3. Additional Analyses

To explore the time point (visit) at which the percent change in body weight from baseline has stabilized and is constant during the 24-week double blind treatment period, two methods will be performed.

- Stepwise tests of linear trend (Maganti et al, 2008) will be performed using a linear mixed model (LMM) approach. The LMM model includes treatment, race (Black or African American, Non-Black or African American), and age (<30, ≥30 years) as fixed effects; visit and treatment-by-visit interaction as random effects; and baseline weight as the covariate. In this model, visit will be treated as a continuous variable. The slope of each treatment group will be estimated from the model. Denominator degrees of freedom will be estimated using the Kenward–Roger approximation (Kenward and Roger 1997). The null hypothesis is that there is no linear trend, ie, the slope of the regression line equals zero. The alternative is that there is a linear trend. The first test of the slope uses the entire range of time points. If the slope is significantly different from zero, the second test excludes the earliest time point. The testing continues, successively excluding the next earliest time point from the start of the study, until the slope is no longer significantly different from zero or until only three time points remain in the model. If the final test is not statistically significant, then the first time point included in that test is considered to be the time point over which a constant weight is attained. If the final test includes three time points and is still statistically significant, then no stable weight is considered to have been attained by the end of the study.
- Helmert contrast (Maganti et al, 2008) will be performed using a similar MMRM approach as outlined in Section 3.8.2.1.2. The first contrast compares the mean change in body weight at the first time point to the pooled mean change in body weight over all remaining time points. The second contrast compares the mean at the second time point to the pooled mean over all remaining time points. Testing continues until the contrast is not statistically significant. The first time point included in this last contrast is concluded to be the time interval on which a stable weight is attained. If the final test is still statistically significant, then no stable weight is considered to have been attained by the end of the study.

3.8.2.2. Primary Efficacy Endpoint: Proportion of Subjects with ≥10% Weight Gain at Week 24 in the FAS Population

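### SAP 3.8.2.1.3: the stepwise linear-trend model has no fixed visit term, so the planned test of zero slope in each arm has no parameter to test

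*SAP*

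**What the plan says.** SAP Section 3.8.2.1.3 states its purpose as "To explore the time point (visit) at which the percent change in body weight from baseline has stabilized and is constant" over the double-blind period, and offers two methods.

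The first is a stepwise test of linear trend from a linear mixed model. Treatment and race are listed with the other terms as follows: "and age (<30, ≥30 years) as fixed effects; visit and treatment-by-visit interaction as random effects; and baseline weight as the covariate". The terms that carry time therefore enter only as "visit and treatment-by-visit interaction as random effects". The time scale is given by "In this model, visit will be treated as a continuous variable". The model's output is given by "The slope of each treatment group will be estimated from the model", and the hypothesis by "The null hypothesis is that there is no linear trend, ie, the slope of the regression line equals zero". For inference, "Denominator degrees of freedom will be estimated using the Kenward–Roger approximation". If the slope is significant, the earliest visit is dropped and the test repeated, until significance is lost or three time points remain.

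The second method uses Helmert contrasts from an MMRM similar to the one in SAP Section 3.8.2.1.2. That section says: "The MMRM model will include treatment, visit, treatment-by-visit interaction term, race (Black or African American, Non-Black or African American) and age", and goes on to class those terms as categorical fixed effects.

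**The concern.** The paragraph assigns every model term to a role, and the two terms that carry time are assigned only to the random part. A random effect describes how units vary around a mean; it does not supply the mean. A model with visit only in its random part allows trajectories to differ but has no average trajectory over time. The analysis needs exactly that average, one per arm.

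At stake is one of the two routes by which the SAP would name the visit from which weight is constant. Each step of the rule turns on whether an arm's mean slope differs from zero. Without a mean slope, the programmer must either depart from the written model or substitute a quantity the SAP does not define.

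**Working it through.** The documents give no figure for this analysis, so there is none to reproduce. The check is algebraic, with a simulation as illustration.

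**1. Mean model as written.** With the listed fixed terms,

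E[Y | covariates, visit] = b0 + b1·treatment + b2·race + b3·age + b4·baseline weight + E[random part].

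The random part contains visit and treatment-by-visit, and its expectation is zero. Visit therefore drops out, and the derivative of the mean with respect to visit is 0 in both arms, by constraint.

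**2. Mean model the test needs.**

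E[Y | ·] = b0 + b1·treatment + b2·race + b3·age + b4·baseline weight + b5·visit + b6·treatment·visit.

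With olanzapine coded 0 and ALKS 3831 coded 1, the slopes are b5 and b5 + b6. The null hypotheses are b5 = 0 and b5 + b6 = 0. Neither coefficient exists in step 1. Kenward–Roger is a correction for inference on fixed effects, so the SAP names an inference method for a parameter its model omits.

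**3. Search for a fixed visit term elsewhere.** No other part of the SAP or protocol adds one to this model. The MMRM of Section 3.8.2.1.2 has fixed visit terms, but it is a separate model with categorical visit.

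**4. Illustration.** Inputs from the documents:
- 200 subjects per arm (SAP Section 2).
- Post-baseline weight at Weeks 1, 2, 4, 6, 8, 12, 16, 20 and 24 (protocol Table 3).
- True slopes from the planning means of 7% and 3%: 7/24 = 0.292 and 3/24 = 0.125 % per week.

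Assumptions of this check, not in the documents:
- Random-intercept SD 1.5, random-slope SD 0.25 (variance 0.25² = 0.0625), residual SD 1.5, and no missing data.
- The written model is read as having subject-level random slopes, with a random intercept added and one slope variance for both arms.

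Fits were by REML, on one simulated data set per scenario, with z ratios in place of Kenward–Roger tests.

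| Quantity | As written | Visit and treatment-by-visit fixed |
|---|---|---|
| Fixed coefficients | intercept, treatment, race, age, baseline weight | the same, plus visit and treatment-by-visit |
| Olanzapine slope | no parameter (mean prediction 0.280) | 0.290, SE 0.019, z = 15.1 |
| ALKS 3831 slope | no parameter (mean prediction 0.101) | 0.105, SE 0.019, z = 5.5 |
| Random-slope variance | 0.117 | 0.069 |

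With true slopes of zero, the fixed-slope model gave z = −0.07 and −1.06, and the random-slope variance was 0.069 under either model.

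The fit as written returned nothing to test. The predictions are shrunk towards zero relative to the fixed estimates: 0.280/0.290 = 0.97 and 0.101/0.105 = 0.96. The mean structure in step 1, and so the conclusion, does not depend on the assumed variances.

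**The case against.** The strongest reply is that the intent is plain. The surrounding sentences, on a continuous visit, a slope per arm, a zero-slope null and Kenward–Roger, make sense only with arm-specific mean slopes. The text probably names the random slopes and omits the matching fixed terms. A model returning no slope would be noticed at programming, and SAP Section 8 leaves programming specifications to a separate document. This stands as a reading of intent and keeps the point minor. It does not cure the text: the terms are explicitly called random, the preceding section calls the same terms fixed where that is meant, and no grouping unit is named. The model should be settled in the SAP.

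A second reply is that arm slopes can be predicted from the random effects. They can, but they are predictions under a model whose mean slope is held at zero, and they do not supply the stated test. If the effects were instead meant at arm level, the treatment-by-visit variance would rest on two levels and the visit variance on one, which is not usefully estimable.

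Three stronger readings are tempting and unsupported:
- *A reader might infer that the analysis would report a slope of zero whatever the data.* A mean constrained to zero is not an estimate. The predicted slopes above were non-zero and followed the data.
- *A reader might infer that all average weight gain is absorbed into the random-slope variance.* The simulation shows that variance rising from 0.069 to 0.117 under an assumed subject-level grouping. It does not show that none of the trend goes elsewhere, and the SAP names no grouping unit.
- *A reader might infer that any stabilisation visit the trial reports is an artefact.* The Helmert method rests on an MMRM with fixed visit and treatment-by-visit terms and is untouched by this defect.

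**Conclusion.** The concern holds for the stepwise linear-trend method only. As written, the model has no population slope in either arm, so the zero-slope test has no parameter and the stepwise rule has no input. This is an error in the specification, not merely missing detail.

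Within that method the defect is total; outside it there is no effect. The analysis is exploratory and lies outside the testing sequence of SAP Section 3.8.4. Both co-primary analyses are unaffected, and the Helmert method can still identify a stabilisation visit.

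The conclusion rests on the standard convention that random effects have mean zero, and on the absence of a fixed visit term for this model anywhere in the two documents. The simulation's numerical values rest on assumed variance components and serve only as illustration.

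**What to change.** In SAP Section 3.8.2.1.3, replace the sentence listing the model terms so that it specifies:
- fixed effects: treatment, race, age, continuous visit and treatment-by-visit, with baseline weight as covariate;
- random effects: a subject-level intercept and a subject-level slope for visit;
- tests: the arm-specific fixed slopes against zero, with the Kenward–Roger degrees of freedom already planned.

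The cost is one sentence and the matching model code. No new data are needed, and no other analysis changes.

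Reporting each arm's slope with its 95% CI at every step would be a useful separate option, since the rule otherwise infers constancy from non-significance alone. It is not needed to repair this defect.

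### Both weight-stabilisation rules in SAP 3.8.2.1.3 read a non-significant test as proof of constant weight, so a weight that is still rising, above all one rising more slowly, can be declared stable

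*SAP*

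**What the plan says.** SAP section 3.8.2.1.3 (Additional Analyses) states its aim: "To explore the time point (visit) at which the percent change in body weight from baseline has stabilized and is constant". It gives two methods.

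- **Stepwise trend test.** A mixed model with visit as a continuous variable gives a slope for each treatment group. The null hypothesis is a zero slope. While the slope is significant, the earliest visit is dropped and the test repeated, down to three visits. If the last test done is not significant, "the first time point included in that test is considered to be the time point over which a constant weight is attained".
- **Helmert contrasts.** Each visit is compared with the pooled mean of all later visits, using a model like the MMRM of section 3.8.2.1.2. "Testing continues until the contrast is not statistically significant", and the first visit in that contrast is taken as the start of stable weight. The text does not say whether the contrasts are run by arm.

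In both methods no stable weight is concluded only if the final test is still significant. Section 3.8.1 fixes the level: "All statistical tests will be 2-sided hypothesis tests performed at the 5% significance level". Neither method sets a margin for a negligible slope or difference, requires a confidence interval, or checks that later visits stay flat.

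**The concern.** A non-significant test shows that a change was not detected, not that there was none. Here non-significance is the success criterion, so the rule rewards imprecision. Precision also falls as the procedure runs. The weight visits in Protocol Table 3 are Weeks 1, 2, 4, 6, 8, 12, 16, 20 and 24. The last trend test therefore uses only Weeks 16, 20 and 24, and the last Helmert contrast only Week 20 against Week 24. The MMRM that the Helmert method follows uses observed on-treatment weights without imputation, so dropout thins those visits further.

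At stake is the statement of when, and whether, weight stabilised on each drug. A 24-week weight trial invites that question, and a named plateau week is easily read as a finding about duration of effect.

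**Working it through.** **Inputs from the documents.** Two-sided 5% tests (SAP 3.8.1); 200 per arm, or 270 if increased, and Week 24 gains of 3% and 7% with a common SD of 9% (SAP 2 and 4); the nine weight visits above (Protocol Table 3).

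**Assumed, because the documents give none.** The shape of the gain curve, the within-subject covariance and the dropout. I varied all three.

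**1. The plan's own figure.** Section 3.8.2.1.3 states no operating characteristics. The only design figure is in section 2: "This sample size will provide at least 90% power to detect a significant difference in mean percent change in body weight" and in the proportion with at least 10% gain. For the means, SE = 9 × √(2/200) = 0.90 and power = Φ(4/0.90 − 1.96) = Φ(2.48) = 0.994. For 14% versus 27%, the pooled test gives 0.899, and other standard formulas give 0.887 to 0.904. The stated 90% is reproduced to within about a point, so the planning inputs are read correctly.

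**2. A curve that is still rising.** Take gain(t) = G × (1 − e^(−t/12)) / (1 − e^(−2)), with G = 3 or 7.
- Weeks 16 to 24: 0.148 × G, or 0.45 points (ALKS 3831) and 1.04 points (olanzapine). The slopes are 0.22 and 0.52 points per 4 weeks.
- Weeks 20 to 24: 0.062 × G, or 0.19 and 0.43 points.

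**3. A floor by hand.** If the final test is non-significant, testing has stopped there or earlier, and either way a plateau is declared. So the chance of a declared plateau is at least the chance that the final test is non-significant. Two assumed covariances, n = 200:
- *Random walk* (variance 81/24 per week, plus error variance 0.25). The SD of the three-visit slope per 4 weeks is √(8 × 81/24 + 0.5)/2 = 2.62, so SE = 0.185. The SD of the Week 20 to 24 change is √(13.5 + 0.5) = 3.74, so SE = 0.265.
- *Random slopes* (SD 9 at Week 24, within-subject SD 1.5). The slope SD per 4 weeks is 4 × √(81 − 2.25)/24 = 1.48. The corresponding SDs are √(1.48² + 1.125) = 1.82 (SE 0.129) and √(1.48² + 4.5) = 2.59 (SE 0.183).

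With z = true change / SE, the chance of non-significance is Φ(1.96 − z) − Φ(−1.96 − z).

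| Final test | ALKS 3831: z, chance | Olanzapine: z, chance |
|---|---|---|
| Trend, random walk | 1.20, 78% | 2.80, 20% |
| Trend, random slopes | 1.73, 59% | 4.03, 2% |
| Helmert, random walk | 0.70, 89% | 1.64, 63% |
| Helmert, random slopes | 1.02, 83% | 2.37, 34% |

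**4. The full rules by simulation.** 1,500 trials per setting, complete data, each arm analysed separately by t-tests on subject-level slopes or contrasts. Ranges are over three covariances (the two types above and a compound-symmetry form), for the 12-week curve.

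| n per arm | Trend: ALKS 3831 / olanzapine | Helmert: ALKS 3831 / olanzapine |
|---|---|---|
| 130 | 73–89% / 11–46% | 94–99% / 55–84% |
| 200 | 61–81% / 2–26% | 89–98% / 34–73% |
| 270 | 48–76% / 0–13% | 84–96% / 22–63% |

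Repeat runs with slightly different settings move the edges by a few points at most. The true curve is the same in every row; only the sample size changes the answer.

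**5. Other shapes, n = 200 (ALKS 3831 / olanzapine).**
- Straight line: trend 3–30% / 0%; Helmert 25–74% / 0–3%.
- Square root: trend 46–76% / 0–10%; Helmert 80–97% / 9–49%.
- Exponential, 8-week constant: trend 83–92% / 32–64%; Helmert 97–100% / 78–94%.

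**6. Does the arm difference hold?** With one SD, equal n and the same shape in both arms, the smaller-gain arm was called constant more often in all 36 settings for each rule. Changing those conditions matters:
- SD scaled to the gain (3.86% on ALKS 3831), trend rule, 12-week curve: the gap narrows to 27% versus 2% (random slopes) and 47% versus 25% (random walk).
- The same with only 100 on olanzapine, random walk: it reverses, 47% versus 56%.
- Olanzapine flattening early (5-week constant) while ALKS 3831 rises in a straight line, random slopes: it reverses, 3% versus 86%.

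**The case against.** The other side has several fair points.

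- **Standing of the analysis.** It is labelled exploratory, is not among the primary, key secondary or other endpoints, and lies outside the testing sequence of SAP 3.8.4. No section plans to compare plateau weeks between arms. This stands and limits the stakes. It does not cure the rule: exploratory status excuses the lack of error control, but it does not turn a non-significant test into evidence of no change.
- **The trajectory is shown anyway.** SAP 3.8.2.1.1 reports weight and percent change at each visit by arm, and 3.8.6 analyses absolute change by visit. A late rise would be visible beside a stable label. This is partial mitigation.
- **The rules do respond to flattening.** A reader might infer that the declared week has nothing to do with whether weight has stopped rising. That goes too far. For ALKS 3831 the trend rule declares a plateau in 3–30% of trials under a straight line and in 83–92% under the 8-week curve. It rarely misses a steady rise at 200 per arm; a slowing rise, and the Helmert rule, are the weak spots.
- **The arm difference is conditional.** A reader might infer that the plan favours ALKS 3831 by design. The documents give no curve shape, and step 6 shows reversals. By-arm estimation is stated for the trend slopes only, so the by-arm Helmert figures rest on a reading that the SAP does not confirm.
- **The simulation is simpler than the SAP's models.** It omits covariates, dropout and the mixed models themselves. The percentages are illustrative, but the direction follows from the rule.

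**Conclusion.** The point stands for the decision rule of both methods: non-significance is equated with constant weight, without a margin, and lower precision makes the claim easier. Under the SAP's planning figures with 200 per arm, and with complete data, a common 12-week exponential shape and the covariances all assumed, a still-rising weight is called constant in roughly 60–80% (trend) and 87–98% (Helmert) of trials on ALKS 3831. On olanzapine the figures are about 1–26% and 34–73%. Reading non-significance as constancy is an error under any of these assumptions. The percentages and the arm difference depend on them, and the latter can narrow or reverse.

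The effect is confined to an exploratory statement about when weight stabilises. A reader might infer a threat to the main result, but the primary and key secondary tests and their Type I error are untouched. The section should be changed before the analysis is run; it is not a barrier to the trial's main conclusions.

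**What to change.** Amend SAP 3.8.2.1.3 as follows.

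1. Do not name a plateau visit on the strength of a non-significant test. Report such a result as *no further change detected*.
2. For each arm, report the mean slope over Weeks 16–24 with its 95% CI, and report the between-arm difference in slope with its CI.
3. If a stability claim is wanted, require the whole CI to lie inside a margin that the sponsor justifies and fixes before unblinding. Do not infer that the arms differ in stability because one meets the margin and the other does not; use the slope difference for that.
4. If the Helmert contrasts are kept as description, say whether they are run by arm.

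**Cost.** A change of wording and a CI in place of a p-value rule; no new data. The drawback is that stability may not be claimable. With 200 per arm and complete data, the half-width is 1.96 × 1.82/√200 = 0.25 to 1.96 × 2.62/√200 = 0.36 points per 4 weeks under the assumed covariances. With 130 remaining it is 0.31 to 0.45.

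The documents give no basis for a margin. Purely as an illustration, with ±0.5 points per 4 weeks and 200 per arm, a truly flat weight would qualify in about 54% (random walk) to 95% (random slopes) of trials. On the 12-week curve ALKS 3831 would qualify in 30–58% and olanzapine in about 2%, although the shape is the same. That is why the margin needs justification and why item 3 bars the between-arm inference.
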